4.3 IXT Symptom Survey Score

A 7-item IXT Symptom Survey will be completed by children aged 5 years and older at the enrollment and 3-month exams. For each IXT-specific symptom, the child is asked how often it occurs, using the response choices of "never" "sometimes", and "all the time." The distribution for each individual item will be tabulated for each treatment group at both baseline and 3 months. The symptom survey will not be Raschscored, and no estimates of between treatment group differences will be obtained.

Children who were less than 5 years old at the time of enrollment will not complete the survey. Instead, they will be asked a single question: "Do you have double vision (see two of things when you know there is really only one)?", with the ability to respond with "never" "sometimes", or "all the time." The distribution

of responses will be tabulated for each treatment group at both baseline and 3 months. No estimates of between treatment group differences will be obtained.

214215216

217

218

219

220

213

4.4 PedEyeQ Score

The PedEyeQ consists of 3 components: child, proxy, and parent. After applying existing Rasch scoring using lookup tables, the average score for each of the domains within the three components will be obtained for each of the treatment groups at 3 months using an ANCOVA model, adjusting for the baseline

domain score. The treatment group difference and 95% confidence interval will be obtained from the

ANCOVA model.

221222223

224

225

4.5 Binocular Diplopia by Parental Report

The number and proportion of participants with binocular diplopia at 3 months with a frequency of "more than 2 times per day" over the last week at distance and near separately (by parental report) will be tabulated by treatment group and analyzed as a dichotomized outcome.

226 227

228

229

230

5 Patch Wear Time

Site staff will activate and distribute occlusion dose monitors (ODMs) for participants randomized to patching (patching adherence is not applicable to the observation group). While activated, the ODM takes a temperature reading every 20 minutes, which is used to determine whether the patch was being worn at that time.

231232

233234

235

The sensors hold 133 days of data when the time interval is set at 20 minutes. If the sensor has not been read and data downloaded for a longer period than the max storage allows (133 days), the oldest data is overwritten, so only the latest 133 days will be uploaded.

236237238

239

For days with sensor readings, the temperature threshold for considering the patch worn will be \geq 82°F (\geq 27.78 °C), versus < 82°F (27.78 °C) for not worn.⁵

For each participant in the full-time patching group, the following statistics will be reported:

240241242

• Number of participants (% of total in patching group) with ODM data.

243244245

 Distribution (median, IQR, minimum, maximum, histogram) of the percentage of days for which ODM data was obtained, including all participants randomized to full-time patching.

246247248

Percentage of days for which ODM data was obtained = (number of days for which ODM data was obtained (regardless of completeness))/(expected number of days of patching) * 100%.

249250251

Expected number of days of patching = (Date of randomization – date of 3-month visit) – 2, since expected to patch day after randomization and stop patching the day before their 3-month visit.

252253

 Number of participants (% of total in patching group) with no ODM data.

254255

Of those with data, the distribution of the number of days patching will be split into quartiles

256257

• Within each quartile, the number of participants (% of total in patching group) will be calculated.

258259

• Distribution (median, IQR, minimum, maximum, histogram) of total number of hours patched in patching group participants with ODM data

260 261 O Total number of hours patched = (Number of readings exceeding 82 degrees Fahrenheit) x 20 minutes x (1 hour / 60 minutes)

262263264

Scatterplots, with Spearman correlation coefficients and 95% confidence intervals, will be generated to illustrate the relationship between the total number of hours patched and each outcome listed below for those with ODM data:

265266

- 267 1. Distance control score
- 268 2. Near control score
- 269 3. Distance angle of deviation
- 270 4. Near angle of deviation
- 5. Suppression Score (0=negligible, 1=mild, 2=moderate, 3=dense)
 - 6. Convergence fusional amplitudes
- 273 7. Divergence fusional amplitudes
 - 8. Symptom Survey Score
 - 9. PedEyeQ score (each domain)

275276277

272

274

The relationship between the total number of hours patched and the suppression score will be illustrated using a boxplot, rather than a scatterplot.

278279280

281

282

283

284

285

286

Patching adherence is categorized by the study coordinator as excellent, good, fair, or poor based on inspection of the patching calendar and discussion with the parent. This data will be tabulated for the 3-month visit, as will the reasons for any major deviations. Descriptive statistics and a boxplot for total number of hours patched as recorded with the ODM by level of patching adherence based on parent report will be obtained.

6 Association of Retinal Correspondence Testing to Other Outcomes

The relationship between retinal correspondence response and each of the following outcomes within each treatment group will be evaluated at 3 months:

287 288 289

290

291

293

294

295

296

- 1. Distance control score
- 2. Near control score
 - 3. Distance angle of deviation
- 292 4. Near angle of deviation
 - 5. Suppression Score (0=negligible, 1=mild, 2=moderate, 3=dense)
 - 6. Convergence fusional amplitudes
 - 7. Divergence fusional amplitudes
 - 8. Diplopia by parental assessment (dichotomized as in section 4.5)
 - 9. PedEyeQ score

Normal retinal correspondence will be defined as correspondence status marked "normal" both when aligned and tropic, while anomalous retinal correspondence will be defined as correspondence status marked "abnormal" when aligned or tropic (or both).

301 302 303

304

305

306

307

308

309

For continuous and ordered categorical outcome variables (control scores, angles of deviation, fusional amplitudes, suppression score, and PedEyeQ score), a difference in means and 95% confidence interval between participants with normal versus anomalous retinal correspondence will be estimated and illustrated using scatterplots (control scores, angles of deviation, fusional amplitudes, PedEyeQ score) or boxplot (suppression score). For categorical outcome variables (diplopia), the difference in proportions and 95% confidence interval between participants with normal versus anomalous retinal correspondence will be estimated by inverting Barnard's test using the method of Agresti and Min.² P-values will not be reported.

310 7 Subgroup Analyses of Distance Control

- The primary analysis will be repeated, stratifying by gender and race/ethnicity subgroups in accordance
- with NIH guidelines, to determine whether treatment effects within subgroups are consistent with overall
- treatment effects. These analyses will include only observed data (no imputed data). No effect modification
- is expected for these factors. A forest plot will be used to display the estimates of difference between
- treatment groups and 95% confidence intervals for each subgroup. P-values will not be reported. Subgroup
- analyses will only be performed for groups with a minimum of 10 observations per group.

317 8 Safety Analyses

- All safety analyses described below will use observed data only without any imputations for missing data.
- Only the visits that occurred within the analysis window will be included.

320321

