3.4 Testing Procedures at 3-Month Outcome Visit

522 The following procedures will be performed in the order specified below at the 3-month outcome
523 visit with the participant wearing their current refractive correction (if worn), and without
524 cycloplegia. If unable to complete the entire masked exam during the office visit, the participant
525 can return with 10 days to complete all masked testing (# 6-14 below). Testing procedures #1-5
526 below do not need to be repeated if completed at the initial office visit.

527

528 1. Adherence Monitoring (for patching group):

- 529 • Evaluate compliance by review of study calendar
- 530 • Download adherence data from ODM

531 2. Eye-Related Quality of life: Pediatric Eye Questionnaire (PedEyeQ)

- 532 • Child questionnaire: Completed by children 5 years and older
- 533 • Parent questionnaire: Completed by the parent for all children regardless of age
- 534 (includes parent and proxy questions)

535 3. Symptom Survey:

- 536 • Intermittent Exotropia Symptom Survey completed by children 5 years or older.
- 537 • Single diplopia question to be completed by children 3 or 4 years.
- 538 4. Diplopia Assessment by Parent: Assess diplopia presence and frequency over the last week,
- 539 by parental report. If present, classify diplopia frequency as “2 times or less per day” or
- 540 “more than 2 times per day.”
- 541 5. Monocular Distance VA Testing: Distance VA testing in each eye using the same test
- 542 method used at enrollment.
- 543 6. Stereoacuity Testing (masked): Randot Preschool Stereoacuity at 40 cm.
- 544 7. Control of the Exodeviation #1 (masked):
- 545 • Distance (6 meters)
- 546 • Near (1/3 meter)
- 547 • The same examiner must assess control for all three assessments of control for each visit.
- 548 8. Divergence Amplitude Testing (masked): Measured at distance (6 meters) using a PEDIG-
- 549 approved prism bar as described in the *IXT7 Procedures Manual*
- 550 • Record the break and recovery points
- 551 9. Convergence Amplitude Testing (masked): Measured at distance (6 meters) using a PEDIG-
- 552 approved prism bar as described in the *IXT7 Procedures Manual*
- 553 • Record the blur, break, and recovery points
- 554 10. Control of the Exodeviation #2 (masked) (repeat) (see item #7)
- 555 11. Ocular Alignment Testing (masked):
- 556 • Testing must be performed by a pediatric ophthalmologist, pediatric optometrist, or
- 557 certified orthoptist.

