986 The distribution of actual patch wear time will be tabulated overall and by treatment groups. The
987 potential correlation between actual patch wear time in the FT patching group and the change
988 from baseline in the following outcomes will be evaluated at 3 months (when collected):

- 989 1. Distance control score
- 990 2. Near control score
- 991 3. Distance angle of deviation
- 992 4. Near angle of deviation
- 993 5. Level of suppression
- 994 6. Convergence fusional amplitudes
- 995 7. Divergence fusional amplitudes
- 996 8. Symptom survey score
- 997 9. Diplopia assessment by Parent
- 998 10. PedEyeQ score (each domain)

999 A Spearman correlation coefficient and 95% confidence interval will be calculated for each
1000 outcome.

1001 **7.8.2 Outcome of Retinal Correspondence Testing**

1002 The relationship of retinal correspondence response with respect to the following outcomes
1003 within each treatment group will be evaluated at 3 months:

- 1004 1. Distance control score
- 1005 2. Near control score
- 1006 3. Distance angle of deviation
- 1007 4. Near angle of deviation
- 1008 5. Level of suppression
- 1009 6. Convergence fusional amplitudes
- 1010 7. Divergence fusional amplitudes
- 1011 8. Symptom survey score
- 1012 9. Diplopia assessment by Parent
- 1013 10. PedEyeQ score

1014 For continuous outcome variables, the difference in means between participants with normal
1015 versus anomalous retinal correspondence will be calculated along with a 95% confidence
1016 interval. For categorical outcome variables, the difference in proportions between participants
1017 with normal versus anomalous retinal correspondence will be calculated along with a 95%
1018 confidence interval.

1019 **7.8.3 Subgroup Analysis of Distance Control**

1020 The treatment group comparison of distance control will be assessed at 3 months in subgroups
 1021 based on gender and race/ethnicity in accordance with NIH guidelines; however, no effect
 1022 modification is expected for these factors.
 1023

1024 **7.9 Safety Analyses**

1025

1026 **7.9.1 Deterioration**

1027 The number and proportion of participants with deterioration, as defined below, will be tabulated
 1028 for each treatment group at 3 months as a safety outcome.

1029 Deterioration is defined as meeting one of the following criteria at the 3 months follow-up visit:
 1030

- 1031 1. Constant exotropia at least 10Δ at distance **AND** near by SPCT:

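### SAP section 5 subtracts the dates for expected patching days in the wrong order, and its wear-time correlations omit the change from baseline that Protocol 7.8.1 specifies

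*SAP*

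**What the plan says.** SAP section 5 (Patch Wear Time) describes how ODM data will be summarised in the full-time patching group. One summary is the distribution of "the percentage of days for which ODM data was obtained, including all participants randomized to full-time patching". Each child's percentage is the number of days with ODM data divided by expected patching days. The denominator is given as "Expected number of days of patching = (Date of randomization – date of 3-month visit) – 2", with the reason "since expected to patch day after randomization and stop patching the day before their 3-month visit". A separate line reports "Number of participants (% of total in patching group) with no ODM data".

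The same section then plans scatterplots and Spearman correlations to "illustrate the relationship between the total number of hours patched and each outcome listed below for those with ODM data". The list names distance control score, near control score, the angles of deviation, suppression, fusional amplitudes and others. Neither the sentence nor the list mentions change.

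Protocol 7.8.1 describes the corresponding analysis as the "potential correlation between actual patch wear time in the FT patching group and the change" "from baseline in the following outcomes will be evaluated at 3 months", followed by a similar list.

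**The concern.** There are two separate problems in one SAP section.

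First, the formula gives a negative number of days for any visit after randomization. The coverage percentage that divides by it cannot be used as written. Coverage matters because total hours depend on how many days the sensor recorded, so a reader needs it to interpret the hours.

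Second, the SAP reads as correlating hours with the 3-month level of each outcome, while the protocol correlates wear time with change. If families of children with worse baseline control patch more, or less, than others, the two analyses give different answers. Protocol 1.6 lists dose-response among the questions left open about patching, so the documents should agree on which correlation addresses it.

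**Working it through.** **Part 1: expected days.** Let V be the days from randomization to the 3-month visit. SAP section 2.1 sets the analysis window at 46 to 137 days. Protocol 3.1 allows 3 months ± 2 weeks, illustrated here by days 77, 91 and 105. The documents give no worked value for the formula, so there is no figure to reproduce.

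- As written: (0 − V) − 2 = −(V + 2).
- Dates swapped, constant 2: V − 2.
- Dates swapped, constant 1: V − 1. This counts from the day after randomization through the day before the visit.

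| V | as written | V − 2 | V − 1 |
|---|---|---|---|
| 46 | −48 | 44 | 45 |
| 77 | −79 | 75 | 76 |
| 91 | −93 | 89 | 90 |
| 105 | −107 | 103 | 104 |
| 137 | −139 | 135 | 136 |

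For a day-91 visit and an assumed 80 ODM days, coverage is 80/(−93) = −86.0% as written, 80/89 = 89.9% with constant 2, and 80/90 = 88.9% with constant 1. With 90 ODM days it is 90/(−93) = −96.8% as written, 90/89 = 101.1% with constant 2, and 90/90 = 100% with constant 1. With no ODM days it is 0 under every version.

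Dropping the minus sign does not repair the formula: 93 days is 4 more than the 89 given by swapping the dates.

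The constant depends on whether the day before the visit counts as a patching day. The SAP's reason and Protocol 2.5.2 can each be read either way, and Protocol 3.1 rules out only the visit day. The difference is one day in about 90, or about 1%.

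**Part 2: level or change.** Protocol Table 1 (section 7.3) shows how far the two measures overlap. Write SDb, SDs and SDc for the SDs of the baseline score, 3-month score and change, with change taken as 3-month score minus baseline. Then cov(b, s) = (SDb² + SDs² − SDc²)/2 and corr(score, change) = (SDs² − cov)/(SDs × SDc).

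- Observation: cov = (1.01² + 1.35² − 1.23²)/2 = 0.665; correlation = (1.8225 − 0.665)/(1.35 × 1.23) = 0.70.
- Part-time patching: cov = (1.00² + 1.23² − 1.38²)/2 = 0.304; correlation = (1.5129 − 0.304)/(1.23 × 1.38) = 0.71.

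About half the variance is shared (0.70² = 0.49; 0.71² = 0.50). These values are approximate, because baseline and 3-month SDs come from slightly different numbers of children.

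The documents give no correlation between wear time and baseline control, so a range was simulated for distance control (4,000 samples of 34 children per setting):

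- From Protocol 7.3: 34 completers per group, SD of change 1.5, and a baseline-change correlation of size 0.30 (negative here, because improvement is negative in the SAP).
- Assumed: baseline mean 2.9 and SD 0.8, clipped to 2–5; wear mean 8 and SD 3.5 hours/day, clipped to 0.2–14; dose-change correlation −0.375; visit day uniform on 77–105; full sensor coverage.
- Total hours = hours/day × (visit day − 1); 3-month score = baseline + change.

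| assumed wear-baseline correlation | mean Spearman, change | mean Spearman, 3-month score | gap |
|---|---|---|---|
| −0.3 | −0.34 | −0.49 | 0.15 |
| −0.2 | −0.34 | −0.44 | 0.10 |
| 0 | −0.34 | −0.36 | 0.01 |
| +0.2 | −0.34 | −0.27 | 0.08 |
| +0.3 | −0.34 | −0.23 | 0.12 |

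Gaps are taken before rounding. The sampling SD of one coefficient at 34 children is about 0.14 to 0.17.

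**The case against.** The reversed dates are plainly a drafting slip. The reason in the same sentence shows that a positive count is meant, and a programmer would notice negative percentages at the first run. SAP section 5 also reports numbers with and without ODM data, total hours, and hours by rated adherence, so coverage is not the only view of wear. All of this stands, and it is why the severity is low. The slip still needs correcting in the text, because whoever repairs it must also settle the constant.

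On the correlations, the objection is that the SAP is silent rather than contradictory. The protocol's list items are also bare outcome names, with change stated only in the lead-in. SAP section 2 defines the primary outcome as a change, and section 3.1 analyses change in near control. That helps for the control scores only. It does not settle angle, suppression, amplitudes or PedEyeQ, and the general text of SAP section 4 allows either the outcome or its change.

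The size of the gap rests on assumed inputs, is negligible with no wear-baseline correlation, and is no more than about one sampling SD anywhere in the range. That also stands.

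A reader might infer three stronger points that the documents do not support:

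- **Coverage is negative for every child with a visit.** Only the denominator is. A child with a visit and no ODM days has coverage 0.
- **The constant 2 is itself an error.** It is correct if the day before the visit is unpatched, and the texts allow that reading.
- **Children with no 3-month visit are overlooked.** They have no visit date for the denominator, but the protocol's 3-month visit procedures include "Download adherence data from ODM", so such a child will usually fall under the line for no ODM data. What remains is a display convention for few children: at the planned 5% loss, about 2 of 36.

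**Conclusion.** Both parts hold and should be corrected at low severity. Taken literally, the expected-days formula gives −48 to −139 days over the SAP's analysis window, and coverage is negative for every child with a visit and at least one ODM day. This follows from arithmetic alone and needs no assumption.

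The SAP's correlation, as worded, is not the one in Protocol 7.8.1. How much that matters is not known from the documents. For distance control, under the stated assumptions, the mean coefficients differ by about 0.01 if wear time is unrelated to baseline control and by up to about 0.15 at an assumed correlation of −0.3.

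Expected days enters only the coverage percentage and no correlation. A reader might take either problem as a threat to the efficacy conclusions. It is not one: wear time enters neither the primary nor the secondary analyses, and Protocol 7.8 lists the correlations as exploratory.

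**What to change.** 1. In SAP section 5, define expected patching days as the 3-month visit date minus the randomization date, less a constant. The sponsor should state the constant and reconcile it with the SAP's own reason and with Protocol 2.5.2 and 3.1: 2 if the day before the visit is unpatched, 1 if it is patched. In the same edit, say how a child with no 3-month visit date appears in the distribution, for example only under the line for no ODM data.
2. In SAP section 5, state that the Spearman correlations use change from baseline in each outcome, as in Protocol 7.8.1. If the 3-month level is intended, record that as a departure from the protocol.

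The cost is two wording corrections and about two lines of code, with no added data, visits or participants.

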199 Previous studies^{22,23,32,33,39,48-50} have shown that the magnitude of the deviation may reduce with
 200 patching treatment. Nevertheless, there are few data that support this notion, and the mechanism
 201 by which patching might alter ocular alignment remains unclear.

202 **1.5 Measuring Patch Wear Time**

203 Adherence with a prescribed patching dose is often problematic and limits the interpretation of
 204 findings when attempting to correlate dose to outcome. In studies of patching treatment for
 205 amblyopia, some research groups have used occlusion dose monitors (ODMs) to record actual
 206 patch wear time.⁵¹⁻⁵⁴ In general these previous studies concluded that dose is a significant factor
 207 in determining amblyopia treatment outcome, although there remains considerable individual
 208 variability. We are unaware of previous studies that have analyzed actual patch wear time when
 209 treating IXT, and such data are important for understanding whether there is a dose effect
 210 relationship.

211 Recently, a new method of monitoring patching adherence has become available and is being
 212 used in a concurrent PEDIG amblyopia study (ATS22, NCT04378790). TheraMon®, a

213 thermosensor device, appears to work well for monitoring adherence with amblyopia patching
 214 treatments in children.⁵¹ We propose utilizing the TheraMon® in the current study to enable
 215 important secondary analyses of outcome in relation to actual (rather than prescribed) wear time.
 216

217 **1.6 Unanswered Questions Regarding Patching Treatment for IXT**

218 While previous data confirm an effect of patching on control of IXT, and even on angle of
 219 deviation, there remain many unanswered questions regarding treatment effectiveness. Such
 220 questions include:

- 221 - Is prescribed full-time patching more effective for improving control and/or reducing
 222 angle of deviation than observation alone?
- 223 - Does patching alter suppression, angle of deviation, fusional amplitudes, or
 224 anomalous retinal correspondence, and are such changes related to exodeviation
 225 control?
- 226 - Is there a dose-response relationship (greater improvement with more actual patching
 227 time)?
- 228 - Which clinical and demographic characteristics, if any, are associated with
 229 improvement in exodeviation control and/or treatment success?

230 **1.7 Rationale for Present Study**

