3.2 Phone Call at 4-weeks

502 Study personnel will call the parent of each participant 4 weeks \pm 1 week following
503 randomization. The purpose of the call for the patching groups is to determine whether patching
504 is being done, and if so, how it is being done. If patching is not being done correctly, patching
505 instructions will be reviewed with the parents. Parents in the patching groups will be asked if
506 they have had any problems using the ODM. If ODMs have been lost, replacement ODMs may
507 be sent to the parent. Parents in both treatment groups will be asked if they have any questions or
508 concerns about the study.

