2.1 Principles to be Followed in Primary Analysis

Model assumptions for ANCOVA will be assessed, including linearity of the adjustment covariates (baseline distance control and distance PACT angle), normal distribution of the outcome, and equal variance in the treatment groups. The linearity assumption of the baseline covariates will be evaluated using scatterplots and by categorizing each of the baseline factors in the ANCOVA model to check for approximate linearity of the coefficients across the ordered categories. Each baseline covariate will be included as a continuous covariate in the model if the assumptions for linearity are met for that covariate; otherwise, the baseline covariate will be categorized.

When three measures of distance control are not performed at the outcome exam, the mean of two measurements, or failing that, a single measurement, will be used if available.

The primary analysis will follow the intention-to-treat principle, with all participants analyzed according to their randomized treatment group, with the following stipulations:

• For participants who receive non-randomized treatment between baseline and 3 months, the distance control score data from the early 3-month visit will be used for the primary outcome. Early outcome visits are not required to fall within the 3-month visit window to be included in analyses.

• Participants who miss the 3-month visit or do not complete any control testing at the 3-month visit, and who do not have an early 3-month outcome visit, will have their mean distance control score imputed using multiple imputation.

• For all participants other than above, to be included in the analysis, the 3-month visit must be completed within the analysis window defined as 46 to 137 days from randomization; otherwise, the distance control at the 3-month visit will be imputed using multiple imputation.

 The multiple imputation for missing data will be performed using Monte Carlo Markov Chain (MCMC) model. (See Section 2.3 below for further details.)

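### SAP Section 5 counts days without sensor data as zero patch wear in the dose-response correlations; coverage-aware versions should be added beside total hours

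*SAP*

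**What the plan says.** SAP Section 5 (Patch Wear Time) defines the exposure as "Total number of hours patched = (Number of readings exceeding 82 degrees Fahrenheit) x 20 minutes x (1 hour / 60 minutes". It then plans scatterplots and Spearman correlations to "illustrate the relationship between the total number of hours patched and each outcome listed below for those with ODM data". Having some ODM data is the only entry condition. The same total is set against coordinator-rated adherence in a boxplot.

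Section 5 also computes the percentage of expected patching days with sensor data. The numerator is the "number of days for which ODM data was obtained (regardless of completeness"), so a day with a few readings counts the same as a full day. This percentage is reported as a separate distribution. It does not enter the exposure, and it does not decide who is included in the correlations.

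The protocol foresees gaps in recording. Section 3.2 says "If ODMs have been lost, replacement ODMs may" be sent to the parent. Neither document says how hours worn with a lost device are to be treated.

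**The concern.** A count of warm readings equals hours worn only if the sensor recorded throughout. Where it did not, the missing hours are scored as unworn, and a child with good wear and poor recording cannot be told from a child with poor wear and good recording. Spearman's coefficient uses only ranks, so each such misplacement feeds directly into the result.

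The protocol has a stake in this. Section 1.6 lists among its open questions "Is there a dose-response relationship (greater improvement with more actual patching" time), and Section 1.5 proposes the sensor so that outcome can be related to actual rather than prescribed wear. A weak correlation from the planned analysis could mean a weak dose effect or incomplete recording, and the planned correlations do not separate the two.

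**Working it through.** **1. Number of children.** Protocol Section 7.3 plans 36 per group and 5% loss: 36 × 0.95 = 34.2, so about 34 patched completers. The plan's figure of 68 completers (34 per group) reproduces: a difference of 1.15, an SD of 1.5 × √(1 − 0.30²) and a two-sided 5% test give 90.4% power with 34 per group in the noncentral-t ANCOVA calculation. The documents state no power or precision for the correlation itself.

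**2. Arithmetic on the SAP formula.** Each reading over the threshold adds 20/60 = 1/3 hour. Take a visit on day 91, so 91 − 2 = 89 expected days.

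- 12 h/day, all days recorded: 12 × 89 = 1,068 h.
- 12 h/day, half the days recorded: 12 × 44.5 = 534 h.
- 6 h/day, all days recorded: 6 × 89 = 534 h.

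The second and third children receive the same exposure although one wore the patch twice as long each day. Ranks can also reverse: 12 h/day with 30 recorded days scores 360 h, below 5 h/day with 90 recorded days at 450 h.

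**3. Effect on the correlation.** The documents give no coverage rate, wear distribution or expected correlation, so all of the following are assumptions: daily wear normal with mean 9 h and SD 3 h, clipped to 0.5–14 h; visits uniform over days 77–105 (about 3 months ± 2 weeks); outcome driven by daily wear with Spearman 0.39; coverage uniform over the stated range and unrelated to wear; 200,000 simulated children. Positive values mean more wear goes with more improvement. Approximate 95% intervals for n = 34 are tanh(atanh(r) ± 1.96 × √(1.06/31)), where √(1.06/31) = 0.185.

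| Exposure | Coverage | Spearman | 95% interval, n = 34 |
|---|---|---|---|
| Daily hours | – | 0.39 | 0.05 to 0.65 |
| Total hours | 100% | 0.37 | – |
| Total hours | 70–100% | 0.36 | 0.01 to 0.63 |
| Total hours | 50–100% | 0.32 | −0.03 to 0.60 |
| Total hours | 30–100% | 0.26–0.27 | −0.10 to 0.56 (at 0.26) |

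The step from 0.39 to 0.37 comes from differing visit dates, not from sensor loss. The rest comes from coverage.

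**4. A second set of assumptions.** Here n = 34, wear is 13 h/day × Beta(2,1), the latent correlation is 0.5 in size, and affected children have a random 10–90% of days recorded. When 0, 10, 20, 30 and 50% of children are affected, the mean Spearman for total hours is 0.44, 0.40, 0.37, 0.34 and 0.29 in absolute value. Hours per covered day stays at 0.47. The direction and rough size agree with step 3.

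**The case against.** **Total hours is a proper cumulative dose.** A reader might infer that it is the wrong exposure because follow-up length varies, the visit having to be "completed within the analysis window defined as 46 to 137 days from randomization". The documents do not support that. Protocol Section 1.6 asks about more actual patching time, and a child seen sooner did receive fewer hours. The simulation in step 3 favours hours per day because it makes daily wear drive the outcome. If cumulative hours drive it instead, with full coverage and visits spread over days 46–137, total hours keeps a Spearman of 0.38 and hours per day falls to 0.28. The two measures answer different questions. This objection stands.

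**Hours per covered day has its own bias.** If the sensor goes missing because patching stopped, the low recorded total is correct and the per-day figure overstates wear. With that mechanism in 20% of children (recorded share 10–90%), total hours gives 0.38 and hours per covered day 0.30. The documents do not say why sensors would be lost. This also stands, and it is the reason not to replace one measure by the other.

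**Early visits.** A reader might infer that symptom-prompted early visits (Protocol Section 3.5) create a false dose-response signal. SAP Section 4 limits exploratory analyses to visits in the analysis window, without the early-visit allowance made in Section 3, and Protocol Section 7.8.1 classes wear time as exploratory. Section 5 does not restate the rule, but on the natural reading visits before day 46 drop out.

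**Sensor storage.** A reader might also point to overwriting after 133 days. Even a day-137 visit exceeds storage by only 137 − 133 = 4 days, which is negligible.

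**Coverage is reported.** The planned distribution of days covered would show whether recording was poor overall. It would not show what the correlation is among well-recorded children, so this answers the point only in part.

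**Conclusion.** The point holds in a limited form. Section 5 scores wear on days without sensor data as zero, and nothing elsewhere in the two documents corrects for it. If loss is unrelated to wear, the correlation is pulled towards zero: from 0.39 to about 0.36 at 70–100% coverage and 0.32 at 50–100%, on assumed inputs. With nearly complete recording and visits in the protocol window the loss is small. With about 34 children the 95% interval has a half-width of about (0.65 − 0.05)/2 = 0.30, so sampling error exceeds these shifts, although they can move a borderline interval across zero.

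The defect is that no coverage-aware analysis stands beside total hours, not that total hours is used. The wear-time analysis is exploratory, so this is a cheap improvement rather than a threat to the trial's conclusions.

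**What to change.** Keep total hours in SAP Section 5 as the cumulative-dose measure, and add:

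- **(a)** the same correlations and the adherence boxplot using mean hours worn per ODM-covered day, or per unit of recorded time so that partial days do not count as full ones. Count only the day after randomization through the day before the outcome visit.
- **(b)** a repeat of the total-hours correlations in children with ODM data on at least a prespecified share of expected days, for example 70%.

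Report all versions together. Agreement would suggest that sensor loss matters little; disagreement would show how far the answer depends on it. State the limits in the SAP: (a) overstates wear if the sensor went missing because patching stopped, and (b) reduces a sample that is only about 34 to begin with.

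The cost is a few sentences and some extra output. The 20-minute readings are already downloaded, and the number of days with ODM data and the expected days are already computed.
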